## **Parent Satisfaction Survey**

A non-standardized 5-point Likert type scale was invented by the investigators to assess compliance and satisfaction with wearing orthosis. Parents were completed the questionnaire PT, 1 MPT and 3 MPT. The items numbered 3, 5 and 7 were questioning about treatment efficiacy while the other items were questioning the ease and utilization of the use of orthosis. That's why to compare all groups only 3.,5. and 7. items were used when all of them were completed for the comparisons of SPIO groups.

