3.03.2017

The Effect of Vest Type Dynamic Elastomeric Fabric Orthosis (DEFO) on Sitting Balance and Gross Manual Dexterity in Children With Bilateral Cerebral Palsy: A Feasibility and Randomized, Single-blinded, Pilot Study (NCT03191552)

(Unique Protocol ID:09.2013.0351)

STATISTICAL PLAN

IBM SPSS Statistics for Windows, Version 20,0 (Armonk, NY, USA) will be used to perform all of the analysis. Statistical significance is accepted as $p < 0.05$. Descriptive statistics will be used to determine mean \pm SD of data. Chi-square and t-tests will be used to compare demographic findings. The histogram and normality plots and Shapiro-Wilk normality test were used for data distribution analysis. Between group analysis will be performed using ANOVA if data followed normal distribution. But if not Kruskal-Wallis test will be performed. Mann-Whitney U test was performed to test the significance of pairwise differences using Bonferroni correction (post-hoc test) to adjust for multiple comparisons. For Bonferroni correction, a p value of less than 0.017 ($0.05/3$) was determined as the level of statistical significance

Depending on the distribution analysis, Wilcoxon and dependent t-test will be utilized to detect within group analyzes. To assume changes over time with treatment Friedman and repeated measures analysis of variance will be conducted.

Mann Whitney u and independent sample t-tests will be applied to compare SPIO 2 hours and 6 hours group. To compare groups in pairs in terms of parent satisfaction questionnaire results chi square test will be done.

To evaluate feasibility, recruitment and retention rates will be calculated and percentages will be reported.

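### The parent survey is compared pair by pair with chi-square, with no all-group test, no correction and no defined set of tests, so its false-positive risk is uncontrolled

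*SAP*

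**What the plan says.** The SAP's Statistical Plan sets a general significance level of 0.05 in its first paragraph. For between-group analysis it then gives an all-group step followed by a corrected pairwise step. The all-group step is ANOVA, or Kruskal-Wallis when the data are not normal: "Between group analysis will be performed using ANOVA if data followed normal distribution". The pairwise step is "Mann-Whitney U test was performed to test the significance of pairwise differences using Bonferroni correction (post-hoc test) to adjust for multiple comparisons", with the level given as "For Bonferroni correction, a p value of less than 0.017", which is 0.05/3.

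The survey appears two paragraphs later, in a sentence of its own: "To compare groups in pairs in terms of parent satisfaction questionnaire results chi square test will be done". No level, item, score or visit is attached to it. The sentence just before it compares the two SPIO groups by Mann-Whitney or t-test, also with no correction.

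The Protocol section on the Parent Satisfaction Survey describes a five-point, investigator-made scale. It says that "to compare all groups only 3.,5. and 7. items were used", that these three items concern treatment efficacy, and that the full set of items serves the comparison of the two SPIO groups. On timing it says "Parents were completed the questionnaire PT, 1 MPT and 3 MPT". The Outcome measures section lists the survey as a secondary outcome.

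**The concern.** The plan recognises that three groups give three pairs and that the level should be divided by three, but it attaches that rule to the Mann-Whitney tests only. The survey sentence goes directly to pairs with a different test. Several items and three visits multiply the number of possible tests, and nothing says which of them count.

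What is at stake is how a single small p-value would be read. Because items 3, 5 and 7 are described as efficacy items, one chance result among many could be reported as parents seeing a benefit of the garment, or of one wearing time. Chi-square also ignores the order of the five answers, and the tables are sparse: a pair has 16 children in 2 × 5 = 10 cells, an average of 1.6 per cell.

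**Working it through.** **1. The plan's own figure.** 0.05/3 = 0.01667, printed as 0.017. This reproduces. For three independent tests, 1 − (1 − 0.017)³ = 0.0501, so the rule does hold one set of three pairs at about 5%.

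**2. Inputs from the documents.** Three groups, so three pairs (Protocol, Study design). Three items compared across all groups, three visits and five answer categories (Protocol, Parent Satisfaction Survey). Planned size 8 per group (Protocol, Sample size). General level 0.05 (SAP).

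**3. Size of the possible test set.**
- One item, or one combined score, at one visit: 3 tests.
- Three items at one visit: 3 × 3 = 9 tests.
- Three items at three visits: 3 × 3 × 3 = 27 tests.
- SPIO-only items come on top. An item numbered 7 exists, so there are at least 7 − 3 = 4 further items, or 4 × 3 = 12 further tests if all are tested at every visit.

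**4. If the tests were independent.** The chance of at least one false result is 1 − 0.95^k: 14.3% for k = 3, 37.0% for k = 9 and 75.0% for k = 27. These overstate the risk, because the tests share children and items and because chi-square is conservative in tables this sparse.

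**5. Simulation allowing for both.** No true difference, 8 per group, Pearson chi-square on the non-empty categories, 8,000 simulated trials per row. The answer distributions and the correlation (between items and between visits, on an underlying normal scale) are assumptions, since the documents give neither. Spread-out answers were taken as uniform (20% in each category) or skewed (2, 5, 13, 40 and 40%).

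| Answers | Correlation | Per test | 3 tests | 9 tests | 27 tests | 27 tests at 0.05/3 |
|---|---|---|---|---|---|---|
| Uniform | 0 | 3.1% | 8.7% | 23.0% | 53.9% | 10.4% |
| Uniform | 0.5 | 3.2% | 8.1% | 22.4% | 52.7% | 10.7% |
| Uniform | 0.8 | 3.0% | 8.1% | 21.4% | 46.9% | 9.2% |
| Skewed | 0 | 3.1% | 7.9% | 21.8% | 52.4% | 14.4% |
| Skewed | 0.5 | 3.0% | 7.9% | 21.9% | 49.4% | 13.2% |
| Skewed | 0.8 | 3.0% | 8.0% | 20.0% | 43.4% | 12.0% |

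**6. Sensitivity to the answers.** Satisfaction answers often pile up at the top. With 60–75% in the top category, the 27-test figure is about 17–41%; it is lower still if the remaining answers are spread evenly, and 6–8% with 85% at the top. In the other direction, if only three or two categories are in use, it rises to 56–67% or 65–83%. Taking spread-out and clustered five-category answers together gives about 7–24% for one visit and about 3–9% for one item at one visit.

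**7. What 0.017 alone would do.** Applied to each pair, it lowers the 27-test figure in the table from 43–54% to 9–14%. Holding all 27 tests at 5% by Bonferroni would need 0.05/27 = 0.00185 per test. The correction therefore helps, but limiting the number of tests matters as well.

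**The case against.** The strongest reply is that the plan is silent rather than permissive. The all-group step is stated for between-group analysis without excluding the survey, and the 0.017 sentence could be read as covering every pairwise test. That reading is possible. However, the 0.017 sentence follows directly on the Mann-Whitney post-hoc tests, and the survey has its own sentence and its own test. That 0.05 applies is an inference, but the more natural one.

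Three stronger readings are tempting, and the documents do not support them:

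- **That the survey is the one uncorrected pairwise comparison.** It is not. The separate SPIO 2 hours against 6 hours tests carry no correction either, and no pairwise procedure is named after ANOVA. The contrast is with the Mann-Whitney post-hoc tests only.
- **That a false survey result is about as likely as not.** This needs all 27 tests, answers spread over the scale and no true difference anywhere. Neither document says that items are tested singly or that every visit is tested.
- **That the Protocol promises an all-group test which the SAP drops.** Its phrase about comparing all groups can simply separate comparisons that include the controls from SPIO-only ones, and three pairwise tests would satisfy it.

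It is also fair to say that the survey is a non-standardised secondary outcome in a feasibility pilot. This limits the consequences, but it does not remove the point, because the SAP commits to significance tests on the survey.

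**Conclusion.** The point holds in this form: the SAP states no all-group test, no multiplicity correction and no defined set of tests for the parent survey. The chance of a false result then depends on choices the plan leaves open, from about 3–9% for one item at one visit to roughly 45–55% for all 27 tests with spread-out five-category answers. These figures assume 8 per group, no true difference, testing at 0.05, and answer distributions and correlations that the documents do not give. The SPIO-only items are not counted in them. The change is worth making because it is cheap and uses rules the SAP already contains. It bears on the survey claims only; the Sitting Assessment Scale analysis and the recruitment and retention rates do not depend on it.

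**What to change.** Replace the survey sentence in the SAP with a short rule:

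1. Name in advance the visit, and the item or score from items 3, 5 and 7, that will be tested. A combined score is suitable only if the items are scored in the same direction. The documents give neither item wording nor scoring direction, so the investigators must confirm this and make the choice; nothing in the documents favours a particular visit or an item mean.
2. Compare the three groups on it with Kruskal-Wallis, which the SAP already uses and which respects the order of the answers. Go to pairs, by Mann-Whitney at 0.017, only if that test is significant.
3. Name one comparison for SPIO 2 hours against 6 hours in the same way.
4. Report all other items and visits as counts by group, with no significance claims.

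The choices should be made without sight of the survey results; otherwise the survey should be reported as exploratory throughout.

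The cost is a few sentences in the SAP and no new data. The downside is that fewer survey results can be called significant. Two named comparisons, each at 0.05, would still carry about 1 − 0.95² = 9.8% between them if independent, which the SAP should state openly.
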